6.4 Accrual Rate

Due to the large volume of NSCLC patients treated at this institution, we generally see 4-5 patients per month that would meet inclusion criteria. Considering those that meet eligibility but do not enroll, we expect an accrual of approximately 2 patients per month.

6.5 Length of Study

In order to accrue 50 patients at a rate specified above, the length of the accrual will be approximately 2 years. The study will complete after the 4-month follow-up of the last patient and we estimate the total duration at no longer than 2.5 years.

A PILOT STUDY OF EXHALED BREATH ANALYSIS TO ASSESS PNEUMONITIS
DEVELOPMENT AFTER CHEMORADIOTHERAPY FOR STAGE III NSCLC
Wake Forest Baptist Comprehensive Cancer Center (WFBCCC)
WFBCCC 98119

7.0 Treatment Plan

7.1 Treatment Administration

This study is observational in nature and does not impact the treatment received by enrolled patients in any way. Patients will be treated according to the standard of care for stage III NSCLC. They will be seen in consultation by a radiation oncologist. When the decision to proceed with definitive CRT is made, patients will sign informed consent for their radiation treatment. They will also sign informed consent for concurrent chemotherapy at the discretion of the medical oncologist.

Treatment planning will comprise a CT simulation with or without contrast using appropriate immobilization at the discretion of the treating radiation oncologist. Methods to account for respiratory motion that may be utilized include 4-dimensional CT imaging and slow CT scan techniques. Target and normal tissue delineation as well as treatment planning will be performed at the discretion of the treating radiation oncologist. Specific radiotherapy dose/fractionation are not mandated by the protocol, but 60-66 Gy in 1.8-2 Gy daily fractions is recommended. Weekly on-treatment visits will be performed according to the standard of care.

Concurrent chemotherapy may be delivered at the discretion of the treating medical oncologist. There is not a mandated time frame for administration of concurrent chemotherapy with regard to the first fraction of radiotherapy, but it is recommended that first dose of concurrent chemotherapy occur within 72 hours of the first radiotherapy fraction – ideally on the same day, if possible.

7.2 Follow-up

After completion of CRT, patients will be followed with routine clinical visits and radiographic examinations according to the standard of care. This observational study utilizes clinical and CT imaging surveillance obtained as part of routine follow-up as outcome measures for SP. Patients will return for post-treatment follow-up visit at 1-month post-treatment for clinical assessment. Serum/EBC samples will be collected at this visit. Three months thereafter, at approximately 4 months post-CRT, a routine surveillance CT examination of the chest (with or without contrast) will be performed. Clinical assessment/follow-up will be performed at this time point as well, and the final sample collection will occur at this visit.

**A PILOT STUDY OF EXHALED BREATH ANALYSIS TO ASSESS PNEUMONITIS
DEVELOPMENT AFTER CHEMORADIOTHERAPY FOR STAGE III NSCLC**
Wake Forest Baptist Comprehensive Cancer Center (WFBCCC)
WFBCCC 98119

7.3 Study Calendar

	Prior to CRT Start	2-week after CRT Start^e	6-week after CRT Start^e	1 Month after CRT End^e	4 Months after CRT End^e
Informed consent	X				
Demographics	X				
Medical history (Appendix E)	X				
Physical Exam	X				
Pulmonary Function Tests (Appendix H)	X ⁱ				
Antibiotic and Steroid Use (Appendix D)	X	X ^e	X ^e	X ^g	X ^g
Smoking Status (Appendix G)	X	X ^e	X ^e	X ^g	X ^g
Breath Collection (EBC ^a /EBV ^{b,h})	X ^d	X ^e	X ^e	X ^g	
Blood collection ^c	X ^d	X ^e	X ^e	X ^g	
CT chest with or without contrast	X				X ^g
Pneumonitis Evaluation (Appendix C)	X			X ^g	X ^g
Dietary Evaluation (Appendix M)	X ^d	X ^e	X ^e	X ^g	
Radiotherapy Detail Form (Appendix I)	X ^f				

^a Approximately 1-1.5 mL of EBC will be generated in 10 min of breathing

^b 500 ml of EBV in each of 4 collection tubes will be collected in 5-7 min of breathing

^c Blood sample in each redtop (x1) and purpletop (x1) vacutainer blood collection tube

^d Pre-CRT sample collections to occur within 14 days of the date of RT start. It is recommended but not required that this occurs on the date of CT simulation.

^e May occur within +/- 7 days of the scheduled time point measured from the date of RT start. The 2-week after CRT start, 6-week after CRT start, and 1-month after CRT time points will be coordinated with routine blood draws through medical oncology by the study research nurse.

^f To be completed after completion of treatment planning. This may also be completed at any time after CRT has started.

^g May occur within +/- 14 days of the scheduled time point measured from the date of RT end.

^h EBV collection is optional, as defined in Section 4.2.2.

ⁱ Pulmonary function tests must have occurred within 1 year of CRT Start. Results of testing performed at Wake Forest sites or other outside facilities is acceptable.

A PILOT STUDY OF EXHALED BREATH ANALYSIS TO ASSESS PNEUMONITIS
DEVELOPMENT AFTER CHEMORADIOTHERAPY FOR STAGE III NSCLC
Wake Forest Baptist Comprehensive Cancer Center (WFBCCC)
WFBCCC 98119

8.0 Specimen Collection and Storage

Detailed descriptions of sample collection, aliquoting and storage are described in Section 4.0. Exhaled breath condensate samples will be aliquoted, stored and secured within a locked freezer at -80° C until analysis.

Exhaled breath volatiles require immediate processing and analysis due to the volatile nature of the sample. As such, these will be batched and processed within 1-2 weeks after collection. Subsequent to this process, no sample will remain in existence. The data generated will be kept in a secure location according to Section 4.3.3 for future exploratory analyses.

Blood samples will be obtained in coordination with routine blood draws that occur as a part of standard of care for patients receiving CRT. Baseline blood will be obtained at the time of CT simulation requiring an additional phlebotomy procedure. The 2-week and 6-week blood samples will be obtained at the time of routine weekly labs (as part of standard monitoring during CRT). The 1-month blood will be obtained at the post-CRT visit, which occurs routinely as part of workup and confirmation of eligibility for consolidation immunotherapy.

To facilitate coordination between breath and blood collection, breath samples will be obtained on the same day as the blood samples, on the day of CT simulation (pre-CRT baseline), on the day of 2-week and 6-week routine on-treatment blood draws, and at the 1-month visit post-CRT.

All samples will be de-identified and stored securely at -80° C in the laboratory of [name]. Samples (non-EBV) will be stored until analysis and remaining samples will be retained indefinitely for future study.

Blood samples will be stored indefinitely in the laboratory of [name] until analyzed. These samples will be de-identified by the unique study ID code given at the time of collection.

9.0 Data Management

Informed consent document	EPIC
Protocol registration form	WISER/OnCore
Medical History	WISER/OnCore
Specimen Collection Form	WISER/OnCore
Antibiotic and Steroid Use (Medications Form)	WISER/OnCore
Tobacco Use Form	WISER/OnCore

A PILOT STUDY OF EXHALED BREATH ANALYSIS TO ASSESS PNEUMONITIS
DEVELOPMENT AFTER CHEMORADIOTHERAPY FOR STAGE III NSCLC
Wake Forest Baptist Comprehensive Cancer Center (WFBCCC)
WFBCCC 98119

Radiotherapy Form	WISER/OnCore
Pneumonitis Form	WISER/OnCore
Research Data	Secure research lab computers and servers

10.0 Confidentiality and Privacy

Confidentiality will be protected by collecting only information needed to assess study outcomes, minimizing to the fullest extent possible the collection of any information that could directly identify subjects, and maintaining all study information in a secure manner. To help ensure subject privacy and confidentiality, only a unique study identifier will appear on the data collection form. Any collected patient identifying information corresponding to the unique study identifier will be maintained on a linkage file, stored separately from the data. The linkage file will be kept secure, with access limited to designated study personnel. Following data collection, subject identifying information will be destroyed. Samples will be de-identified and stored indefinitely in a secured wake forest laboratory. Consistent with data validation and study design, producing an anonymous analytical data set. Data access will be limited to study staff. Data and records will be kept locked and secured, with any computer data password protected. No reference to any individual participant will appear in reports, presentations, or publications that may arise from the study.

11.0 Data Safety and Monitoring

The principal investigator will be responsible for the overall monitoring of the data and safety of study participants. The principal investigator will be assisted by other members of the study staff.

12.0 Reporting of Unanticipated Problems, Adverse Events or Deviations

Due to the observational nature of this study, adverse events of interest are limited to those that occur in the immediate duration of the non-invasive exhaled breath collection itself. Should an AE related to breath collection occur, the investigators will notify study staff for logging in the Adverse Event Log (Appendix L).

Any unanticipated problems, deviations or protocol changes will be promptly reported by the principal investigator or designated member of the research team to the IRB.

12.1 Adverse Event Definitions

12.1.1 Adverse Event (AE)

A PILOT STUDY OF EXHALED BREATH ANALYSIS TO ASSESS PNEUMONITIS
DEVELOPMENT AFTER CHEMORADIOTHERAPY FOR STAGE III NSCLC
Wake Forest Baptist Comprehensive Cancer Center (WFBCCC)
WFBCCC 98119

An adverse event (AE) is defined as any unexpected, unfavorable or unintended condition that occurs immediately during the exhaled breath condensate or exhaled breath volatile collection (while the collection device is applied to the patient).

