4.2.3 Blood Collection

Patients treated with CRT have blood counts checked prior to CRT and weekly during CRT to ensure their eligibility for concurrent chemotherapy.

A PILOT STUDY OF EXHALED BREATH ANALYSIS TO ASSESS PNEUMONITIS
DEVELOPMENT AFTER CHEMORADIOTHERAPY FOR STAGE III NSCLC
Wake Forest Baptist Comprehensive Cancer Center (WFBCCC)
WFBCCC 98119

This is part of routine standard of care in medical oncology. Additionally, routine blood count testing is performed approximately 1 month after completion of CRT, to ensure eligibility for consolidative immunotherapy as per the standard of care. In order to minimize the number of blood draws the patients are subjected to, we will plan to obtain research blood samples simultaneously with clinical blood draws at baseline (visit prior to CRT which will occur at the time of the RT planning CT simulation), the last blood draw within 1 week of the last fraction of RT, and at follow-up approximately 1 month after completion of CRT. With the patient's consent, we will obtain 1 x purple-top vacutainer EDTA tube and 1 x red-top tube in conjunction with these standard blood draws.

All samples collected from this study will be banked and will have the potential to be used for future scientific experimentation, which may include additional genetic, proteomic, and metabolomic analyses not described in the data collection section below.

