12.1.2 Serious Adverse Event (SAE)

A serious adverse event (SAE) is any untoward medical occurrence that occurs during the exhaled breath condensate or exhaled breath volatile collection (while the collection device is applied to the patient) that satisfies any of these criteria: results in death; is life-threatening; requires inpatient hospitalization or prolongs existing hospitalization; results in persistent or significant disability or incapacity or substantial disruption of the ability to conduct normal life functions; or if the event results in a congenital anomaly or birth defect.

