12.4 STRC SAE Reporting Requirements

The Data Safety Monitoring Committee (DSMC) is responsible for reviewing SAEs for WFBCCC Institutional studies as outlined in Appendix N. All Adverse Events that occur during protocol intervention and are coded as either 1) unexpected grade 4, 2) unplanned inpatient hospitalization \geq 24 hours (regardless of grade), or grade 5 (death) must be reported to the DSMC using the SAE console in WISER.

All WFBCCC Clinical Protocol and Data Management (CPDM) staff members assisting a Principal Investigator in investigating, documenting and reporting an SAE qualifying for DSMC reporting are responsible for informing a clinical member of the DSMC as well as the entire committee via the email notification procedure of the occurrence of an SAE.

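### The AE and SAE definitions stop when the breath device comes off, so later-onset harm from breath collection and harm from any study-added blood draw fall outside the AE log and DSMC reporting

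*Combined protocol and SAP*

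**What the plan says.** Three places in the protocol set the scope of adverse-event capture.

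- Section 12.0 cites the observational design and states that "adverse events of interest are limited to those that occur in the immediate duration of the non-invasive exhaled breath collection itself". It then gives the trigger for logging: "Should an AE related to breath collection occur, the investigators will notify study staff for logging in the Adverse Event Log".
- Section 12.1.1 defines an AE as a condition that "occurs immediately during the exhaled breath condensate or exhaled breath volatile collection (while the collection device is applied to the patient".
- Section 12.1.2 starts its SAE definition from "any untoward medical occurrence that occurs during the exhaled breath condensate or exhaled breath volatile collection", with the same condition that the device is on the patient, and then lists the usual seriousness criteria.

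Later sections build on these terms. Section 12.2 tells staff what to enter in the AE Log when an AE occurs. Section 12.4 sends certain events to the DSMC, beginning from "All Adverse Events that occur during protocol intervention". Section 12.5 is wider. It requires prompt IRB reporting of unanticipated problems as well as adverse events, and it names procedures among the possible sources of a reportable event.

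On blood sampling, Section 8.0 says: "Baseline blood will be obtained at the time of CT simulation requiring an additional phlebotomy procedure". Section 4.2.3, aiming to keep the number of draws down, says: "we will plan to obtain research blood samples simultaneously with clinical blood draws at baseline".

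**The concern.** The observational design is a good reason not to collect adverse events of standard chemoradiotherapy and immunotherapy, which the study does not assign. It is not a reason to leave out procedures that the study itself adds. The definitions use a strict time window on one procedure, so they miss two things:

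- an event that breath collection causes but that starts after the mask or tube is taken away;
- any event from a blood draw done only for the study, whenever it starts, unless it happens to coincide with breath collection.

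At stake is how complete the AE log and the DSMC's view are for the study's own procedures. No biomarker estimate or test depends on it.

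**Working it through.** The protocol gives no figure to reproduce here. The check sets the sections side by side and then counts occasions.

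**Step 1: is the limit a slip in one sentence?** No. Sections 12.0, 12.1.1 and 12.1.2 all confine the scope to breath collection, and the two definitions add that the device must be on the patient. No other section in the available text extends either definition to blood collection.

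**Step 2: do the sections agree with each other?** Not fully. The logging sentence in Section 12.0 is causal (related to breath collection), while Sections 12.1.1 and 12.1.2 are temporal (device applied). Take a reaction that breath collection causes but that begins a minute after removal. It passes the causal test and fails the temporal one. Because the logging sentence speaks of an AE, the definition has to be met first, so the event is not logged.

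**Step 3: what inherits the definition?** Recording under Section 12.2 begins when an AE occurs. DSMC reporting under Section 12.4 covers Adverse Events meeting certain grade or hospitalization conditions. An event that is not an AE enters neither.

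**Step 4: what remains?** Section 12.5 covers unanticipated problems, including those arising from procedures, whether or not the AE definition is met. Unexpected harm from a blood draw therefore has a written route to the IRB. An anticipated complication of venepuncture, such as a haematoma or vasovagal reaction, is not clearly covered.

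**Step 5: does the study add a draw?**

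| Source | Baseline draw |
|---|---|
| Section 8.0 | An additional phlebotomy at CT simulation; the other three samples are tied to routine labs or the routine post-CRT visit |
| Section 4.2.3 | Taken with a clinical draw, at the visit when CT simulation takes place |
| Section 7.3, footnote e | Names the 2-week, 6-week and 1-month draws as coordinated with routine blood work ("1-month after CRT time points will be coordinated with routine blood draws through medical oncology by the study research nurse"); baseline is not named |
| Section 7.3, footnote d | Pre-CRT samples within 14 days of RT start; the simulation day is recommended but not required |

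Footnote e fits Section 8.0. Footnote d leaves room for some baseline samples to coincide with a routine pre-treatment draw. The documents do not settle the question.

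**Step 6: count.** Planned patients: 50 (Sections 4.2.1 and 6.1). Baseline draws: 1 per patient.

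- If Section 8.0 governs everywhere: 50 × 1 = 50 added draws.
- If Section 4.2.3 governs everywhere: 50 × 0 = 0 added draws.

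The range is 0 to 50. The gap after device removal does not depend on this question and applies to every breath collection. These are counts of procedures, not of expected events; the documents give no complication rate.

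**The case against.** The strongest reply is that the scope is deliberate. Section 12.0 gives a reason for it, Section 7.1 says the study does not affect treatment, and breath collection is what is new for the patient. Venepuncture is minor, and unexpected harm from it would go to the IRB under Section 12.5. The principal investigator is also responsible for participant safety overall (Section 11.0). Most of this stands, and it keeps the point small. It does not explain why a study-added needle stick should be left out, or why an event that breath collection causes should cease to be an AE once the device is off.

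Three stronger readings are tempting, and the documents do not support them.

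- A reader might infer that every patient has a research-only phlebotomy, about 50 in all. That rests on Section 8.0 alone. Section 4.2.3 contradicts it, and footnote d of the calendar allows other timing. Fifty is an upper bound.
- A reader might infer that such harm cannot be recorded anywhere. Section 12.5 gives a route for unanticipated problems. The AE Log form (Appendix L) and the DSMC appendix (Appendix N) are not in the available text, so what they would accept cannot be checked. The attribution scale in Section 12.3 refers to the study collection without restricting it to breath. What can be said is that the written definitions do not require these events to be logged.
- A reader might infer that an empty log would undermine a safety conclusion of the trial. None is planned: Sections 2, 5 and 6 contain no safety or tolerability objective, outcome or analysis.

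**Conclusion.** The point holds as a gap in safety capture. As written, harm that begins just after device removal, even if breath collection caused it, and harm from any blood draw the study adds lie outside the AE log and DSMC reporting. Unanticipated problems still reach the IRB.

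The part about device removal rests only on the wording of Sections 12.0, 12.1.1 and 12.1.2. The part about blood draws also depends on whether the baseline draw is additional. Sections 8.0 and 4.2.3 disagree on that, so between 0 and 50 draws are affected at the planned 50 patients. That contradiction needs correcting in its own right.

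The importance is low. This is a cheap improvement to safety capture; no planned biomarker, microbiome or metabolomic result changes.

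**What to change.** 1. Reword Sections 12.0, 12.1.1 and 12.1.2 so that AEs and SAEs include events during, or directly following, any procedure done only for the study, namely breath collection and any additional blood draw. Using the same wording in all three also removes the mismatch between the causal trigger and the time window. Sections 12.2 and 12.4 then follow without further edits.
2. Reconcile Section 4.2.3 with Section 8.0 on whether the baseline draw is additional, and make the calendar footnotes agree with the answer.

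The cost is one phrase in each of three sections, one correction on blood sampling, and a few extra log entries. Sample size, visits and analyses are unaffected.

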12.1.2 Serious Adverse Event (SAE)

A serious adverse event (SAE) is any untoward medical occurrence that occurs during the exhaled breath condensate or exhaled breath volatile collection (while the collection device is applied to the patient) that satisfies any of these criteria: results in death; is life-threatening; requires inpatient hospitalization or prolongs existing hospitalization; results in persistent or significant disability or incapacity or substantial disruption of the ability to conduct normal life functions; or if the event results in a congenital anomaly or birth defect.

12.2 Recording Adverse Events

When an AE occurs, it is the responsibility of the Investigator to review all documentation (e.g., medical progress notes, laboratory, and diagnostics reports) relative to the event. The study staff will then record all relevant information regarding an AE in the AE Log (Appendix L).

12.3 Adverse Event Characteristics

- **CTCAE term (AE description) and grade:** The descriptions and grading scales found in the revised NCI Common Terminology Criteria for Adverse Events (CTCAE) version 5.0 will be utilized for AE reporting. All appropriate treatment areas should have access to a copy of the CTCAE version 5.0. A copy of the CTCAE version 5.0 can be downloaded from the CTEP web site (<http://ctep.cancer.gov>).
- **‘Expectedness’:** AEs can be ‘Unexpected’ or ‘Expected’ (see Section 7.1 above) for expedited reporting purposes only.
- **Attribution** of the AE:
 - Definite – The AE **is clearly related** to the study collection.
 - Probable – The AE **is likely related** to the study collection.
 - Possible – The AE **may be related** to the study collection.
 - Unlikely – The AE **is doubtfully related** to the study collection.
 - Unrelated – The AE **is clearly NOT related** to the study collection.

A PILOT STUDY OF EXHALED BREATH ANALYSIS TO ASSESS PNEUMONITIS
DEVELOPMENT AFTER CHEMORADIOTHERAPY FOR STAGE III NSCLC
Wake Forest Baptist Comprehensive Cancer Center (WFBCCC)
WFBCCC 98119

12.4 STRC SAE Reporting Requirements

The Data Safety Monitoring Committee (DSMC) is responsible for reviewing SAEs for WFBCCC Institutional studies as outlined in Appendix N. All Adverse Events that occur during protocol intervention and are coded as either 1) unexpected grade 4, 2) unplanned inpatient hospitalization \geq 24 hours (regardless of grade), or grade 5 (death) must be reported to the DSMC using the SAE console in WISER.

All WFBCCC Clinical Protocol and Data Management (CPDM) staff members assisting a Principal Investigator in investigating, documenting and reporting an SAE qualifying for DSMC reporting are responsible for informing a clinical member of the DSMC as well as the entire committee via the email notification procedure of the occurrence of an SAE.

